11.1 Data Analysis

We will summarize the response experience of the patients with percentages and confidence intervals. (We will not adjust for the interim analysis when computing the confidence intervals.) We will define overall survival as the time from the start of treatment until death from any cause. Patients who leave the study and whose survival status we cannot determine will be censored at the last date they were known to be alive. Progression-free survival will be the time from the start of treatment until disease progression or death from any cause. Patients who start non-protocol therapy in the

absence of disease progression will be considered to have progressed on the date the new therapy begins. If the patient is lost to follow up, the patient's time to progression will be censored at the last date they were known to be alive and disease free. Duration of response will be defined as the time from the first known response until disease progression, with death not related to disease censoring this endpoint. All failure-time endpoints will be analyzed with appropriate statistical methods for censored data. We will estimate the distributions of times until the events by the method of Kaplan and Meier. We will fit the proportional hazards model to learn about associations of patient or tumor characteristics with failure-time endpoints. Data displays will include summary statistics and confidence intervals.

Correlative analyses (e.g., laboratory correlates of response, such as PD-L1 expression, presence of TILs, and changes in immune markers) will be exploratory

Safety Analysis

All patients who receive any study treatment will be included in final summaries of safety data. Summaries of AEs and other safety parameters will be provided as appropriate. Summary tables for extent of exposure to study treatment will also be provided.

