10.1 Definitions

10.1.1 *Evaluable for toxicity*

All patients will be evaluable for toxicity from the time of their first treatment on protocol.

10.1.2 *Evaluable for objective response*

For each, only those patients who have measurable disease present at baseline, have received at least one cycle of therapy, and have had their disease re-evaluated will be considered evaluable for response. These patients will have their response classified according to the definitions stated below. (Note: Patients who exhibit objective disease progression prior to the end of the first cycle of either therapy will also be considered evaluable.)

10.1.3 *Evaluable Non-Target Disease Response*

Patients who have lesions present at baseline that are evaluable but do not meet the definitions of measurable disease, have received at least one cycle of therapy, and have had their disease re-evaluated will be considered evaluable for non-target disease. The response assessment is based on the presence, absence, or unequivocal progression of the lesions.

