11. STATISTICAL CONSIDERATIONS

The primary outcome of this study is overall response rate (CR+PR via RECIST 1.1). We will use a Simon's optimal 2-stage design with 80% power and 5% one-sided type-I error to compare the null hypothesis of ORR=5% vs. the alternative of ORR=20%. The first stage will enroll 10 patients, and if 1 or more responses are observed an additional 19 patients will be enrolled. If at least 4 responses are observed out of the 29 patients, the null hypothesis will be rejected

Safety Monitoring: We will monitor adverse events (AEs) throughout the study. If it appears that the risk of a serious AE is excessive, we will evaluate the treatment regimen and either modify the treatment plan or consider stopping the study. The risk of a serious AE (or DLT as defined above) is excessive if the risk is greater than 25%. Our stopping criterion corresponds to our determining that there is 75% or greater probability that the risk of a DLT exceeds 25%. Experience with single-agent anti-PD1 therapy suggests that the risk of a serious AE is between 15% and 20% but may be higher with the combination. We characterize this estimate with uncertainty using a beta distribution with parameters 2 and 8. This distribution has mean 0.2 and 90% probability that the risk is between 4% and 43%. The following table shows the stopping boundaries for safety monitoring.

Number of patients experiencing a DLT	4	5	6	7	8	9	10	11
Number of patients treated	4 - 6	7 - 9	10 - 13	14 - 17	18 - 20	21 - 24	25 - 27	28 - 29

Estimates of the operating characteristics for this stopping rule, as estimated from 5,000 simulations for each scenario, are as follows.

Risk of DLT	0.10	0.15	0.20	0.25	0.30	0.35	0.40	0.45	0.50
Chance of declaring the combination too toxic	1.2	4.8	14.2	31.2	51.7	71.5	86.9	94.9	98.3
Average sample size	28.8	28.1	26.6	24.0	20.8	17.2	13.7	11.1	9.1

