11.2 Interim Analysis

The first stage will enroll 10 patients, and if 1 or more responses are observed an additional 19 patients will be enrolled. After the first 6 patients are accrued, the regimen will be evaluated for toxicity. If 2 or more patients experience a DLT, the study will be halted for excess toxicity.

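### Does leaving the response-rate interval unadjusted for the interim look put it at odds with the two-stage test?

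*Combined protocol and SAP*

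**What the plan says.** Section 11 sets the test: "We will use a Simon's optimal 2-stage design with 80% power and 5% one-sided type-I error", comparing the "null hypothesis of ORR=5% vs. the alternative of ORR=20"%. Section 11.2 repeats the stage rule: "The first stage will enroll 10 patients, and if 1 or more responses are observed an additional 19 patients will be enrolled". Section 11 then gives the final rule: "If at least 4 responses are observed out of the 29 patients, the null hypothesis will be rejected".

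Section 11.1 covers reporting: "We will summarize the response experience of the patients with percentages and confidence intervals". A parenthesis follows: "We will not adjust for the interim analysis when computing the confidence intervals". Neither section 11.1 nor any other part of the document gives a confidence level or an interval method for the response rate. Nowhere is an interval used to judge the null hypothesis.

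**The concern.** The test and the interval treat the same data differently. The test counts the early stop at 0/10 as part of the design; the interval acts as if 29 patients had been enrolled in one step. Here that matters for the level of the test, because without the stop the cut-off of 4/29 would exceed 5%. An exact interval that ignores the stop can therefore contain 5% when the rule has just rejected 5%.

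It would happen at 4/29, the smallest success the trial can declare and the result a reader is most likely to check. The report could then say that 5% is rejected and print a lower limit of 4.9% beside it. With level and method left open, someone could also choose the interval after seeing the count.

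**Working it through.** **Inputs.** From sections 11 and 11.2: 10 patients in stage 1, stop at 0 responses, 19 more otherwise, reject at 4 or more of 29, null 5%, alternative 20%. Assumption not in the plan: a two-sided 90% level, chosen because it corresponds to a one-sided 5% test.

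**1. The stated design.** Let X1 be the stage 1 responses and S the total. Summing over X1 = 1 to 10:

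- P(X1 ≥ 1 and S ≥ 4) = 0.0468 at 5% and 0.801 at 20%.
- A search over two-stage designs for the smallest expected sample size under the null returns these same stage sizes and cut-offs.

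The stated 5% level and 80% power are reproduced.

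**2. What the early stop contributes.** Ignoring it, P(Bin(29, 0.05) ≥ 4) = 0.0548. The difference is the chance of 0/10 followed by 4 or more in the next 19: 0.95^10 × P(Bin(19, 0.05) ≥ 4) = 0.5987 × 0.0132 = 0.0079, and 0.0548 − 0.0079 = 0.0468 to rounding of the last digit. This is the whole source of the exact-interval mismatch.

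**3. Intervals at 4/29 (13.8%).** The two-stage exact lower limit solves P(X1 ≥ 1 and S ≥ 4) = a. The upper limit solves P(X1 = 0) + P(X1 ≥ 1 and S ≤ 4) = a. Here a = 0.05 for 90% and 0.025 for 95%.

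| Interval at 4/29 | 90% | 95% |
|---|---|---|
| Exact (Clopper-Pearson), unadjusted | 4.85–28.84 | 3.89–31.66 |
| Exact, two-stage | 5.11–30.78 | 4.09–34.27 |
| Wilson | 6.35–27.42 | 5.50–30.56 |
| Jeffreys | 5.93–26.75 | 4.84–29.54 |
| Wald | 3.26–24.33 | 1.24–26.34 |

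- At 90%, adjustment moves the exact lower limit by 5.11 − 4.85 = 0.26 points.
- At 95%, the exact interval contains 5% with or without adjustment, so adjusting does not remove the mismatch.
- The Wald interval also contains 5% at 90%, but that comes from the normal approximation and not from ignoring the interim look.
- Wilson and Jeffreys 90% intervals exclude 5% with no adjustment at all.

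**4. Neighbouring results.** At 5/29 the unadjusted exact 90% lower limit is 7.05%. At 4/28, which would arise if one patient were not evaluable under section 10.1.2 and were left out, it is 5.03%. Neither contains 5%.

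**5. How often.** The chance of exactly 4/29 after continuing is 3.4%, 14.3%, 17.3% and 12.0% at true rates of 5%, 10%, 15% and 20%.

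**6. Coverage of the unadjusted exact interval.** This uses Clopper-Pearson on S/29, or on 0/10 if stopped, at 1,181 true rates from 1% to 60%.

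- Over 5% to 20%, coverage is 94.2% to 98.8% at the 90% level and 96.8% to 99.4% at the 95% level.
- It falls below nominal at 2 of 1,181 points for 90% (minimum 87.9%) and 17 for 95% (minimum 93.9%), all above the 20% alternative.
- Over 5% to 20%, the unadjusted 90% upper limit falls below the true rate at most 1.4% of the time, against a nominal 5%. It first exceeds 5% at a true rate of about 26%.

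**7. Cost of adjusting.** The exact 90% upper limit rises from 28.8% to 30.8% at 4/29, from 24.6% to 28.2% at 3/29, and from 15.3% to 26.0% at 1/29. The last is almost the limit for 0/10 (25.9%), although the observed rate at 1/29 is 3.4%.

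**The case for a change.** The strongest case for a change is about consistency and specification in advance. The mismatch falls on the smallest declarable success. Among trials that reject, exactly 4/29 accounts for 0.143/0.289 = 49% at a true rate of 10% and 0.120/0.801 = 15% at 20% (0.289 is the rejection probability at 10%, from the same enumeration). Declaring that there will be no adjustment does not settle level or method, and at 4/29 the 90% methods divide over whether 5% lies inside. Naming both would cost one clause.

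The facts in this stand: level and method are not given, and an exact 90% interval at 4/29 would contain 5%. What does not follow is that the plan is wrong. A descriptive interval need not invert the test, and no choice of interval can alter a decision fixed by a count. The mismatch also needs several things together: a 90% level, an exact or Wald method, exactly 4 responses, exactly 29 patients, and limits printed to at least one decimal (4.85% rounds to 5%). Naming a level and method, with a note that the count rule governs, would be tidy drafting, but the trial can be analysed and read correctly without it.

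**Conclusion.** The concern does not call for a change. Leaving the interval unadjusted is a declared and fair trade-off. The section 11 rule and its error rates (0.0468 and 0.801) are untouched, and the unadjusted exact interval is conservative over the 5% to 20% range for which the trial is designed. The two-stage interval would gain 0.26 points on one lower limit at one result and would give upper limits that are harder to explain at low counts. The unstated level and method are a gap that any competent analyst fills.

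This rests on the planned 10 + 19 enrolment being attained and on the interval serving only as description. The size of the mismatch also assumes a 90% level. If 4/29 occurs and an exact 90% interval is reported, one sentence saying that the two-stage count rule is the test is enough.

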1.3 Secondary Endpoints

1.1.1 *Progression free survival*

Progression-free survival will be measured from the time of study enrollment until radiologic, clinical progression or death.

1.1.2 *Duration of response*

Time (time of first response until progression).

1.1.3 *Overall survival*

Overall survival will be measured from the time of enrollment until death.

1.1.4 *Safety and tolerability*

Toxicities observed in the study will be assessed by CTCAE 5.0 criteria.

1.1.5 *Laboratory correlates of response*

1.1.5.1 **PD-L1 expression pre and post treatment**

1.1.5.2 **Presence of TILs (tumor infiltrating lymphocytes) pre and post treatment**

1.1.5.3 **Assessment of immune markers in pre-treatment fresh and post-treatment biopsies and blood.**

1.1.5.4 **Assessment of genomics and tumor mutation burden in select patients.**

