4.2 Treatment period

One cycle is 21 days. Patient will remain on treatment as long as they are obtaining clinical benefit with a PR, CR or SD as per RECIST 1.1 criteria, and are without significant toxicity requiring treatment discontinuation.

4.3 Post-Treatment Tumor Follow-up – Once treatment on protocol has discontinued, no further tumor assessments are necessary. The last obtained CT on protocol will be utilized for response assessments.

4.4 End-of-Treatment Visit – This will be planned if feasible within 2 weeks of discontinuation of therapy.

4.5 Long-Term Survival Follow-Up – patients will be followed for survival for 1 year after discontinuation of treatment. Review of medical records or phone calls would be sufficient.

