10.5 Duration of Response

10.5.1 Duration of overall response:

The duration of overall response is measured from the time measurement criteria are met for CR or PR (whichever is first recorded) until the first date that recurrent or progressive disease is objectively documented (taking as reference for progressive disease the smallest measurements recorded since the treatment started).

The duration of overall CR is measured from the time measurement criteria are first met for CR until the first date that progressive disease is objectively documented.

10.5.2 Duration of stable disease:

Stable disease is measured from the start of the treatment until the criteria for progression are met, taking as reference the smallest measurements recorded since the treatment started, including the baseline measurements.

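### Duration of response censors deaths judged unrelated to disease, so its Kaplan-Meier estimate overstates time alive and in response if any responder dies that way

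*Combined protocol and SAP*

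**What the plan says.** Duration of response is a secondary endpoint, and the combined protocol and SAP describes it in three places.

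- Section 1.3 (item numbered 1.1.2): "Time (time of first response until progression". Death is not mentioned.
- Section 10.5.1: from the date response criteria are first met "until the first date that recurrent or progressive disease is objectively documented". Death is not mentioned, and progression must be objectively documented.
- Section 11.1: the clock runs from first known response to progression, and a further clause covers deaths: "with death not related to disease censoring this endpoint". This implies, without saying so, that a disease-related death is an event.

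Section 11.1 names one estimator for all time-to-event endpoints: "We will estimate the distributions of times until the events by the method of Kaplan and Meier". It gives no criterion or adjudication process for relatedness, no competing-risk estimate, and no sensitivity analysis with death as an event.

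On PFS, the same section says: "Progression-free survival will be the time from the start of treatment until disease progression or death from any cause". On scans, section 4.3 says: "Once treatment on protocol has discontinued, no further tumor assessments are necessary". Survival follow-up continues for one year after treatment stops (section 4.5).

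**The concern.** A responder who dies of toxicity, infection or another cause cannot progress afterwards. Censoring that patient in a Kaplan-Meier analysis treats the response as one that could have continued, so the death never lowers the curve. Duration of response is usually read as time alive and in response, and for that quantity the curve is then too high.

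Three features of the plan add to this. First, relatedness is undefined, so an unguided judgement decides whether a death is an event or a censoring. Where a responder stops treatment without progression and dies later, the protocol requires no scan that could inform the judgement. Second, a fatal toxicity in a responder would be a PFS event and a censored duration of response on the same day. Section 11 itself allows that serious adverse events may be more frequent with the combination than with single-agent anti-PD-1 therapy. Third, the three definitions differ, so two analysts could get different results from the same data.

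**Working it through.** **Number of responders.** The plan gives no figure for duration of response. Its response design shows how few patients will carry the estimate. Section 11 specifies a "Simon's optimal 2-stage design with 80% power and 5% one-sided type-I error", with response rates of 5% (null) and 20% (alternative), 10 then 19 patients, continuation on at least 1 response, and success on at least 4 of 29.

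P(success) = Σ over x = 1 to 10 of C(10,x) p^x (1−p)^(10−x) × P[Bin(19,p) ≥ 4−x]

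- p = 0.05: 0.0468, within the 5% limit.
- p = 0.20: 0.8011, meeting 80% power.

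A search for the smallest expected sample size under the null returns the same design, so the stated figures reproduce. Expected responders with all 29 enrolled are 29 × 0.20 = 5.8 at the alternative and 29 × 0.05 = 1.45 at the null. Success needs 4. The median may therefore rest on about 4 to 6 patients.

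**Direction.** Take untied times and let n_i be the number at risk at the i-th ending. The risk sets are the same under both rules. Counting every death multiplies the curve by (1 − 1/n_i) at each unrelated death; censoring omits that factor. The censored curve is therefore never below the any-death curve. It is above it from the first unrelated death until both reach zero.

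**Size (assumed inputs).** The documents give neither a rate of unrelated death among responders nor hazards for duration of response. Assume constant hazards λp for progression and λd for unrelated death, and let f = λd/(λp+λd).

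- Censored median = ln 2/λp
- Progression-or-death median = ln 2/(λp+λd)
- Ratio = (λp+λd)/λp = 1/(1−f)

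With an illustrative progression-only median of 6.0 months, the censored analysis gives 25.0% still in response at 12 months whatever f is.

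| f | Progression-or-death median (months) | Censored median longer by | Progression-or-death, in response at 12 months |
|---|---|---|---|
| 0% | 6.0 | 0% | 25.0% |
| 5% | 5.7 | 5% | 23.2% |
| 10% | 5.4 | 11% | 21.4% |
| 20% | 4.8 | 25% | 17.7% |
| 30% | 4.2 | 43% | 13.8% |

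**One death in a small sample.** Suppose all responders are followed to an ending.

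- Six responders, all endings counted: the curve runs 5/6, 4/6, 3/6, so the median is the 3rd ordered time. If the first ending is a censored unrelated death, it runs 4/5, 3/5, 2/5 at the 2nd, 3rd and 4th times, and the median moves to the 4th. The same shift follows if the censored death is the 2nd or 3rd ending. There is none if it is the 4th or later.
- Four responders: one censored death among the first two endings moves the median from the 2nd to the 3rd ordered time.

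**The case against.** The strongest reply is that this is a choice of estimand. All three sections run the endpoint to progression, and section 11.1 only adds what happens at an unrelated death. If the target is time to progression with such deaths removed, and those deaths are independent of progression risk, the censored estimate is right for that target. This stands in part. A reader might take the 5% to 43% figures as bias from informative censoring. They are not: the constant-hazard model makes the two risks independent, so the figures measure the gap between two estimands. The documents contain nothing from which to estimate dependence. Equally, they neither state that hypothetical target nor support the independence it needs.

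Second, the deaths are not lost to view. PFS and overall survival count death from any cause, section 7.1.1 records the fatal condition as the adverse event, the safety summaries cover every treated patient, and toxicity stopping rules exist. That is correct. A reader might infer that the plan conceals toxic deaths, and it does not. The defect is confined to duration of response.

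Third, a reader might infer that open-label knowledge of treatment biases a comparison. The study has one arm, so there is no between-arm contrast to distort. The narrower point remains: an undefined judgement can lengthen the reported duration.

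Fourth, the endpoint is secondary, with no hypothesis, threshold or decision rule. That limits the consequence but does not remove the problem.

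**Conclusion.** The concern holds in conditional form. If at least one responder dies of a cause classed as unrelated to disease, the planned estimate overstates time alive and in response, and the direction of that error is certain. If none does, the effect is zero. It would go too far to say that the reported duration will be overstated by a known amount, because f is not in the documents and every percentage above rests on assumed constant hazards. With about 4 to 6 responders the practical risk is that classifying one early death shifts the median by one ordered time.

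The difference from PFS is a difference between two endpoint definitions, not an arithmetical contradiction, but the plan gives no reason for it. The primary response-rate test and the first-stage rule are unaffected. The point is worth correcting because the endpoint is named, the present rule can only lengthen the estimate relative to counting every death, and nothing elsewhere in the plan offsets it.

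**What to change.** In section 11.1, define duration of response as the time from first documented response to progression or death from any cause, whichever comes first. Censor patients alive without progression at their last tumor assessment. Put the same definition in section 1.3 (item 1.1.2) and section 10.5.1.

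Two further rules are needed for the definition to work:

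- State whether the rule that treats the start of non-protocol therapy as progression, given in section 11.1 next to PFS, also applies to duration of response.
- State how a death long after the last scan is handled. Section 4.3 requires no scans after treatment stops, so an event dated at death would otherwise credit an unscanned interval as response.

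Keep the present censoring rule only as a sensitivity analysis, with a written criterion for a death unrelated to disease.

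The cost is a small wording amendment to both protocol and SAP text. Sections 1.3 and 10.5.1 are protocol sections, so the amendment needs IRB approval under section 12.7. It needs no additional patients, visits or data. The reported duration may be shorter.

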11.2 Interim Analysis

The first stage will enroll 10 patients, and if 1 or more responses are observed an additional 19 patients will be enrolled. After the first 6 patients are accrued, the regimen will be evaluated for toxicity. If 2 or more patients experience a DLT, the study will be halted for excess toxicity.

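### The toxicity operating characteristics in Section 11 leave out the Section 11.2 halt at 2 or more DLTs in the first six patients, and no figures are given for the two rules together

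*Combined protocol and SAP*

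**What the plan says.** Section 11 (Statistical Considerations) monitors toxicity throughout. The prior is explicit: "We characterize this estimate with uncertainty using a beta distribution with parameters 2 and 8". The criterion is a posterior probability of at least 75% that the DLT risk is above 25%. A boundary table follows, starting at 4 DLTs in 4 to 6 patients and ending at 11 in 28 to 29. The response to excessive risk leaves room for judgement, since ending the trial is only one of its options: "If it appears that the risk of a serious AE is excessive, we will evaluate the treatment regimen and either modify the treatment plan".

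The operating characteristics come directly after the boundaries: "Estimates of the operating characteristics for this stopping rule, as estimated from 5,000 simulations for each scenario, are as follows". The row "Chance of declaring the combination too toxic" reads 1.2, 4.8, 14.2, 31.2, 51.7, 71.5, 86.9, 94.9 and 98.3% at DLT risks 0.10 to 0.50 in steps of 0.05. Average sample size runs from 28.8 down to 9.1.

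Section 11.2 (Interim Analysis) adds a second rule: "After the first 6 patients are accrued, the regimen will be evaluated for toxicity". It continues: "If 2 or more patients experience a DLT, the study will be halted for excess toxicity". This halt leaves no room for judgement. The document does not say how it fits with Section 11 and gives no operating characteristics that include it.

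On the monitored event, Section 11 says: "The risk of a serious AE (or DLT as defined above) is excessive if the risk is greater than 25" per cent. No section defines a DLT or a period for assessing one.

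**The concern.** At six patients the two sections give different instructions. With 2 or 3 DLTs, Section 11 lets the trial continue and Section 11.2 halts it. Read together, the trial stops if either rule fires. The only published stopping chances and average sample sizes would then be those of one component, and they would understate how often the trial ends for toxicity. The efficacy decision is set for 29 patients, so an investigator, IRB or DSMB relying on the table would think completion likelier than it is.

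**Working it through.** **Inputs.** From Section 11: prior Beta(2,8), threshold 25%, posterior cut-off 75%, printed boundaries, maximum 29 patients. From Section 11.2: halt at x ≥ 2 when n = 6. Assumptions: DLTs are independent, DLT status is known for all six at the look, any stop is final, and there is no futility stop.

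**Step 1: boundary implied by the criterion.** After x DLTs in n patients the posterior is Beta(2+x, 8+n−x). The smallest x with P(risk > 0.25) ≥ 0.75, from patient 4, is 3 at n = 4; 4 at 5–8; 5 at 9–11; 6 at 12–15; 7 at 16–19; 8 at 20–22; 9 at 23–26; 10 at 27–29.

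**Step 2: reproduce the stated table.** Let f(n,x) be the probability of being unstopped with x DLTs after n patients. Then f(n,x) = (1−p)·f(n−1,x) + p·f(n−1,x−1), removing mass at or beyond the boundary after each patient. Without the six-patient halt, stopping is 1.0, 4.9, 14.7, 31.5, 52.3, 72.0, 86.3, 94.6 and 98.3%. Average N is 28.79, 28.10, 26.55, 23.99, 20.68, 17.12, 13.84, 11.15 and 9.11. Every stopping chance is within 0.65 points of the stated one (at most 1.3 simulation standard errors for 5,000 runs), and every average N is within 0.15. The stated table is therefore the 75% criterion alone, with no futility stop.

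**Step 3: the six-patient look alone.** P(X ≥ 2) = 1 − (1−p)^6 − 6p(1−p)^5. At p = 0.20 this is 1 − 0.2621 − 0.3932 = 34.5%. At 0.10, 0.15, 0.25 and 0.30 it is 11.4, 22.4, 46.6 and 58.0%. Each exceeds the stated total at that risk, so the table cannot include the look.

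**Step 4: both rules.** The same recursion, with an added stop at n = 6 if x ≥ 2:

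| DLT risk | Stated stop % | Both rules % | Stated N | Both rules N |
|---|---|---|---|---|
| 0.10 | 1.2 | 11.5 | 28.8 | 26.4 |
| 0.15 | 4.8 | 23.1 | 28.1 | 23.8 |
| 0.20 | 14.2 | 37.4 | 26.6 | 20.7 |
| 0.25 | 31.2 | 53.5 | 24.0 | 17.5 |
| 0.30 | 51.7 | 69.6 | 20.8 | 14.4 |
| 0.35 | 71.5 | 82.9 | 17.2 | 11.7 |
| 0.40 | 86.9 | 91.9 | 13.7 | 9.5 |
| 0.45 | 94.9 | 96.8 | 11.1 | 7.8 |
| 0.50 | 98.3 | 99.0 | 9.1 | 6.7 |

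At risk 0.20 the halt adds 37.4 − 14.7 = 22.7 points over the exact criterion, or 37.4 − 14.2 = 23.2 over the stated figure.

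**Step 5: the disagreement at n = 6.** P(risk > 0.25) is 0.461 after 2 DLTs in 6, 0.686 after 3 and 0.852 after 4. Only the last meets 75%.

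**Step 6: printed boundaries.** They ask for one DLT more than the criterion at many sample sizes. For example, 4 DLTs in 7 gives 0.81 and 4 in 8 gives 0.765, yet the table requires 5. Run alone, the printed boundaries stop 8.0% at risk 0.20 and 96.4% at 0.50, against 14.2% and 98.3% stated. With the halt added they give 11.5, 22.6, 35.8, 50.5, 65.4, 78.8, 88.9, 95.1 and 98.3%, with average N 26.4, 23.8, 20.9, 17.9, 15.0, 12.3, 10.1, 8.4 and 7.3.

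**Step 7: effect of the Simon futility stop.** If response and DLT are independent, the trial ends at patient 10 with probability 0.95^10 = 0.599 at ORR 5% and 0.80^10 = 0.107 at ORR 20%, when toxicity has not already stopped it. At DLT risk 0.20, average N under the criterion plus the halt becomes about 13.5 and 19.4; the toxicity stopping chance becomes 35.7% and 37.1%.

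**The case against.** The strongest reply is that nothing in the table is false. It sits directly under the Bayesian rule, is labelled as belonging to that rule, and does not claim to describe the whole trial. The halt is in plain view in Section 11.2. A strict early check beside looser continuous monitoring is a legitimate choice, so a posterior of 46% at 2 of 6 is not in itself a mistake. All of this stands. It does not remove the gap, because these are the only toxicity operating characteristics offered and they are not those of the trial as written.

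A reader might infer more than the documents support:

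- *That the design is unsafe or the efficacy test compromised.* The halt only adds stopping, so it favours patients and cannot raise type I error.
- *That 23 to 37% is the expected stopping chance.* The 15 to 20% range in Section 11 is a serious-AE risk for single-agent therapy, not a DLT risk for the combination. At an assumed DLT risk of 5% the look halts only 3.3% of trials. The plan does, however, apply its Beta(2,8) prior, with mean 0.2, to the DLT criterion.
- *That the combined average Ns are the sizes to expect.* They ignore futility stopping, as the stated table does; Step 7 shows how much that matters.
- *That every halt at 2 or 3 DLTs in 6 is an extra stop.* At risk 0.20 those outcomes make up 31.1 of the 37.4 points, but some of these trials would have stopped later anyway. The net addition is 22.7.
- *That subtracting the stated table from the printed-boundary results isolates the halt.* It mixes in the boundary mismatch. Against the printed boundaries alone, the halt adds 35.8 − 8.0 = 27.8 points at risk 0.20.

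**Conclusion.** The point holds as a gap in reporting and specification, worth fixing. The Section 11 table covers the 75% posterior criterion only. With the mandatory halt included, the chance of a toxicity stop is higher by about 10 points at DLT risk 0.10, 23 at 0.20, 18 at 0.30 and under 1 at 0.50. Average N is lower by 2.4 to 6.5 patients. The printed boundaries are a second, separate inconsistency, since they do not deliver the stated table even without the halt. The conclusion at risk 0.20 does not depend on which boundary governs: 37.4% or 35.8%, against 14.2% stated.

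The figures assume that DLT status is known for all six at the look. Section 11.2 ties the look to accrual and gives no assessment window. If status were known for only five or four, the look would fire in 26.3% or 18.1% of trials at risk 0.20 rather than 34.5%. The practical size also depends on a DLT definition that the document does not contain.

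**What to change.** 1. State in Section 11.2 that the 2-of-6 halt applies in addition to Section 11, governs at n = 6, and is assessed once DLT status is known for all six. Add it to the boundary table.
2. Make the printed boundaries match the 75% criterion (Step 1), or name the printed ones as governing.
3. Reissue stopping chances and average N for the combined rule under the chosen boundary (Step 4 or Step 6). Label them as ignoring the Simon futility stop, or give them at ORR 5% and 20%.
4. Define the one DLT that both rules count, and point the Section 11 cross-reference to it.

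If the halt was not intended, delete it from Section 11.2 and correct the printed boundaries, so that the present table holds.

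The cost is a few sentences, a revised boundary table and a re-run of the simulation, with no extra patients. If the halt stays, the published stopping chances and average sample sizes become less favourable.
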